Study Protocol Title:

A Prospective Pilot Study to Evaluate Efficacy and Safety of Euflexxa for the Treatment of Osteoarthritis

Principal Investigator: [name] **[contact]

Funding Sponsor:

Ferring Pharmaceuticals, Parsippany, NJ

Project Contact: [name]

Senior Director, Medical Affairs – Orthopaedics

Ferring Pharmaceuticals Inc.

[name]

[contact] [contact]

:

Regulatory Sponsor:

This study is an Investigator Initiated research trial. Each study site will be considered its own regulatory sponsor and is responsible for internal data monitoring and any study reporting required by ClinicalTrials.gov.

Introduction

Knee osteoarthritis is one of the most common joint disorders which affects a large portion of aging population¹. One of the treatment options is viscosupplementation, which is intra-articular injection of hyaluronic acid IA-HA. Multiple studies have been conducted on the safety and efficacy of IA-HA, but none of the studies, to our knowledge, have evaluated the synovial fluid markers. Therefore, it becomes essential to investigate the effect of IA-HA on the concentration of various synovial fluid markers.

Background and Significance

The FLEXX trial² was the first well-controlled, randomized, double-blind, multicenter study evaluating the efficacy of Euflexxa (1% sodium hyaluronate) therapy for knee osteoarthritis. Five-hundred-and-eighty patients were randomized to receive either Euflexxa or normal saline. There were significant improvements in the Visual analogue scale score Osteoarthritis Research Society International responder index, HRQoL, and function at 26-week follow-up². However, the FLEXX trial did not evaluate changes in synovial fluid bio-marker levels.

The hypothesis of this study is that Euflexxa therapy for knee osteoarthritis will improve levels of inflammatory and degenerative synovial fluid bio-markers in patients with knee osteoarthritis. In addition, we also hypothesize that Euflexxa therapy will improve pain, clinical outcomes, and time to total knee arthroplasty.

Study Design

Methods

- A prospective pilot study

Sample

- 25 subjects for a pilot study

Inclusion criteria:

- 1) OA of the knee by American College of Rheumatology criteria
- 2) Those who failed non-pharmacological measures or simple analgesics
- 3) moderate to severe pain score of 41 to 90 mm recorded on 100-mm visual analog scale (VAS) immediately following a 50-foot walk

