- 4) bilateral standing anterior-posterior radiograph demonstrating Kellgren and Lawrence grade 2 or 3 OA of the target knee
- 5) ability and willingness to use only acetaminophen as the analgesic (rescue) study medication
- 6) unassisted walking 50 feet on a flat surface and going up and down stairs
- 7) willingness and ability to complete efficacy and safety questionnaires

Exclusion criteria:

1. Age less than 18 years
2. any major injury to the target knee within the prior 12 months
3. any surgery to the target knee within the prior 12 months
4. surgery to the contralateral knee or other weight-bearing
5. inflammatory arthropathies
6. gout or pseudogout within the previous 6 months
7. radiographic acute fracture, severe loss of bone density, avascular necrosis, and/or severe bone or joint deformity in the target knee

8. osteonecrosis of either knee
9. fibromyalgia, pes anserine bursitis, lumbar radiculopathy, and/or neurogenic or vascular claudication
10. target knee joint infection or skin disorder/ infection within the previous 6 months
11. symptomatic OA of the hips, spine, or ankle; known hypersensitivity to acetaminophen, IA-BioHA, or phosphate-buffered saline solution
12. Women of childbearing potential who are pregnant, nursing, or planning to become pregnant, and those who do not agree to remain on an acceptable method of birth control throughout the study
13. history of immune disorders; vascular insufficiency of lower limbs or peripheral neuropathy
14. current treatment or treatment of cancer within the previous 2 years (excluding basal cell or squamous cell carcinoma of the skin)
15. active liver or renal disease
16. any clinically significant abnormal laboratory value [to be defined in detail at a later point]
17. any intercurrent chronic disease or condition that might interfere with the completion of the study
18. participation in any experimental device study within the prior 6 months or any experimental drug study within the prior month

Research Procedures – Define the data to be collected to answer the hypothesis/research question(s)

Injection:

Twenty five patients will be assigned to receive Euflexxa (n=10) (1% sodium hyaluronate). Three consecutive injections (2 sets) will be performed with 1 weeks' time in-between each injection at the index visit (Index visit, Week 1±3 days and Week 2±3 days) and at six months (6 month, Week 7, and Week 8).

Aspiration (primary outcome)

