Knee joint aspiration will be performed prior to the initial injection (at visit 1), and at visit 4 (6 weeks \pm 1 week) and visit 6 (6-months \pm 2 weeks) as outlined in previous studies which measured synovial fluid biomarkers.^{3,4} Following aspiration, the synovial fluid will be placed on ice as soon as possible, and transported to the lab. In the lab it will be centrifuged at 1,500 rpm for 10 minutes at a temperature of 4°C. Subsequently, the supernatant fluid will be removed and 1mL of Trizol will be added to the cell pellet (sediment). The pellet will be stored at -20°C and shipped to Rush University Medical Center for future RNA sequencing analyses (cell markers and TLR/Nfk-b Pathway genes). The results of these tests (RNA sequencing) will not be shared with the patients, and will not be documented in the medical record.

The supernatant fluid will be used for biomarker analysis. Remaining fluid will be frozen and stored for future research. The purpose of the aspiration is to measure the following synovial fluid bio-markers^{3,4}:

Biomarker	Measurement Method
1. Chondroitin 6-sulfate (C6S)	FACE ¹ and sizing
2. Chondroitin 4-sulfate (C4S)	FACE and sizing
3. Keratan sulfate (KS)	FACE and sizing
4. Hyaluronate (HA)	FACE and sizing
5. Matrix metalloproteinase-3 (MMP-3)	ELISA ²
6. Tissue inhibitor of MMP-1 (TIMP-1)	ELISA
7. Tissue Necrosis Factor-alpha (TNF- α)	ELISA
8. IL-6	ELISA
9. Tumor necrosis factor-stimulated gene 6 (TSG-6)	ELISA
10. Inter alpha inhibitor (IaI)	Western Blot

¹ FACE- Fluorophore-assisted carbohydrate electrophoresis

² ELISA – Enzyme-linked immunosorbent assay

Secondary outcome measurements⁵

- The effect of Euflexxa on pain, using the Visual Analogue Scale (VAS)
- The effect of Euflexxa on Clinical outcomes using the following standardized scales and questionnaires:
 1. Western Ontario and McMaster Universities Arthritis Index (WOMAC)
 2. Knee Society Score (KSS)
 3. Veterans Rand-12 item form (VR-12)
 4. UCLA activity score (UCLA)
- Time to total knee arthroplasty, which will be collected by asking questions regarding whether or not the patient received a total knee arthroplasty will be asked at each visit (Knee surgery?)(**Table 1**).

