Visual analogue scale (VAS), Western Ontario and McMaster Universities Arthritis Index (WOMAC), Knee Society Score (KSS), Short Form-12 (SF-12), UCLA activity score (UCLA), and questions regarding whether or not the patient received a total knee arthroplasty will be asked at each visit (**Table 1**).

	Index visit /Visit 1	Visit 2 (Week 1 ± 3 days)	Visit 3 (Week 2 ± 3 days)	Visit 4 (Week-6±2 weeks) (visit 4)	Visit 5 (3- month±2 weeks)	Visit 6 (6- month±4 weeks)	Visit 7 (One week from visit 6 ± 3 days)	Visit 8 (Two weeks from visit 6 ± 3 days)	Visit 9 (1-year±2 months)	Visit 10 (2- year±2 months)
Aspiration	X			X		X				
Injection	X	X	X			X	X	X		
VAS	X	X	X	X	X	X			X	X
WOMAC	X	X	X	X	X	X			X	X
KSS	X	X	X	X	X	X			X	X
SF-12	X	X	X	X	X	X			X	X
UCLA	X	X	X	X	X	X			X	X
Knee Surgery?	X	X	X	X	X	X			X	X
Adverse Events	X	X	X	X	X	X	X	X	X	X

The subjects will be paid a stipend of 40 dollars for each visit (visit 1 to visit 10). Thus, a total of 400\$ will be paid to the patient if all the visits are completed. Additionally, the subjects will be provided free parking for all the visits.

Research Protocol Guidelines (continued)

Data Analysis

Unless otherwise indicated, all testing of statistical significance will be two-sided, and a difference resulting in a p-value of less than or equal to 0.05 will be considered statistically significant. Also, after each analysis, General Linear Models (GLM) will be used to control for possible confounders, including BMI, gender, age and ethnicity.

Adverse Events and Data Monitoring Committee(DMC)

Procedural safety will be documented in this study through patient and surgeon reported adverse events. AEs will be documented for all cases in this study.

An Unanticipated Problem Involving Risks to Participants or Others is any event that (1) is unforeseen, (2) caused harm or placed a person at increased risk of harm, and (3) is related to the research procedures.

An Adverse Event (AE) is any untoward or unfavorable medical occurrence, including any abnormal sign (for example, abnormal physical exam or laboratory finding), symptoms, or disease. Adverse events can encompass both physical and psychological harms.

An Internal Adverse Event (AE) is an untoward medical occurrence, which occurs to participants in research conducted by Cleveland Clinic and/or Cleveland Clinic is the IRB of record.

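### The primary outcome is ten unranked synovial markers at two later visits, each judged at p ≤ 0.05, with no lead marker, success criterion, multiplicity rule or exploratory label

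*Combined protocol and SAP*

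**What the plan says.** Background and Significance states a directional hypothesis: "Euflexxa therapy for knee osteoarthritis will improve levels of inflammatory and degenerative synovial fluid bio-markers". Study Design gives the sample as "25 subjects for a pilot study".

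Under Research Procedures, the aspiration subsection carries the primary label: "Aspiration (primary outcome". It continues: "The purpose of the aspiration is to measure the following synovial fluid bio-markers". A table of ten markers follows, numbered but not ranked. On timing it says: "Knee joint aspiration will be performed prior to the initial injection (at visit 1), and at visit 4" (6 weeks), and then at visit 6 (6 months). Each marker therefore has one baseline value and two later values. Table 1 shows that visit 6 is also the first injection visit of the second course.

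Data Analysis is two sentences long. The first makes testing two-sided unless otherwise indicated, and adds that "a difference resulting in a p-value of less than or equal to 0.05 will be considered statistically significant". The second adds a general linear model after each analysis, to control for BMI, gender, age and ethnicity. Nothing is otherwise indicated for the markers. The document names no test for them and has no lead marker, primary visit, success criterion, multiplicity rule or exploratory label.

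**The concern.** The primary hypothesis concerns a whole panel, but the only decision rule applies to one comparison at a time. Suppose one marker of ten reaches p ≤ 0.05 at one of two visits. The plan allows that marker to be called statistically significant. It does not say whether the result supports the hypothesis, is neutral, or is about what chance would produce. The same gap leaves open which marker and which visit will be put forward once the data are in.

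The cost falls mainly on what comes next. A pilot is often used to choose the endpoint for a larger study, and a marker chosen because it crossed 0.05 among ten or twenty looks is a weak basis for that choice.

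**Working it through.** There is no stated figure to reproduce. The 0.05 threshold is stipulated, and the 25 subjects come with no power, effect size, standard deviation or dropout.

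**Inputs from the document.** Ten markers; two visits after baseline; two-sided threshold 0.05; 25 subjects. The Injection paragraph gives both twenty-five and n=10 for the same group. Those figures must be reconciled, so both are shown.

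**Assumptions.** One-sample t-test on each change from baseline; complete data; correlation 0.5 between the two visits' changes; correlation between markers from 0 to 0.9; no true change in any marker. The count is 10 (one test per marker) or 20 (one per marker and visit).

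**Step 1: independent tests.** The chance of at least one p ≤ 0.05 is 1 − 0.95^k.
- k = 10: 1 − 0.95^10 = 0.401
- k = 20: 1 − 0.95^20 = 0.642, with 20 × 0.05 = 1 false positive expected

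**Step 2: correlated tests.** Simulation, 20,000 runs, at least one p ≤ 0.05 in either direction:

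| Marker correlation | 10 tests, n=25 | 20 tests, n=25 | 10 tests, n=10 | 20 tests, n=10 |
|---|---|---|---|---|
| 0 | 40.6% | 62.2% | 40.5% | 62.5% |
| 0.3 | 35.4% | 55.8% | 36.6% | 57.7% |
| 0.5 | 29.4% | 47.6% | 30.4% | 49.1% |
| 0.8 | 17.9% | 30.4% | 19.1% | 32.2% |
| 0.9 | 12.8% | 22.4% | 14.0% | 24.4% |

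Using one omnibus test over both visits per marker (ten tests, n=25) gives 40.4% down to 13.8%, much the same as one visit per marker.

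**Step 3: improvement only.** The hypothesis is that levels improve, so a significant worsening cannot support it. Assume one direction of improvement per marker and count only results in that direction, so that a single test has a 2.5% chance. Under independence:
- k = 10: 1 − 0.975^10 = 0.224
- k = 20: 1 − 0.975^20 = 0.397

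Simulated at n=25 with the same correlations, the range is about 6-23% for 10 tests and 12-37% for 20. The plan assigns no direction of improvement to any marker, so this too is an assumption.

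**Step 4: precision if the panel is reported descriptively.** The half-width of a 95% interval for mean change, in SDs of the change, is t(0.975, n−1)/√n.
- n = 25: 2.064/5 = 0.41 SD
- n = 10: 2.262/3.162 = 0.72 SD

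**The case against.** The best defence is that this is a pilot. The title and the design say so, there are 25 subjects, and the Introduction speaks of investigating the effect on various markers. On that view the panel is there to be described, and the 0.05 sentence is a reporting convention, not a success rule. Much of this stands. The word pilot, however, describes the study and not how its p-values will be read. The title also promises an evaluation of efficacy, the hypothesis is directional, and the threshold covers all testing unless otherwise indicated. If the panel is meant to be exploratory, one sentence would say so, and that sentence is missing.

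A second objection is that the error rate depends on a criterion the plan never states. This is also fair. Requiring at least three of the ten markers, for example, would bring the either-direction chance down to about 1-7% in the same kind of simulation at n=25. But the plan states no such criterion.

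Three stronger readings are tempting, and the documents do not support them:
- **That any one significant marker makes the trial positive.** Data Analysis defines when a difference is called significant. It does not define when the study succeeds.
- **That there are more than twenty primary tests because four markers are measured by sizing as well.** The phrase "FACE and sizing" appears only as a measurement method. Nothing says that it yields a separately tested result.
- **That the either-direction figures are the chance of falsely claiming improvement.** They include worsening. The improvement-only figures are roughly half as large.

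**Conclusion.** The concern holds as a gap in the decision rule for the primary outcome. If no marker changes from baseline, applying the stated threshold to each comparison gives at least one significant marker in about 13-41% of studies (10 tests) or 22-62% (20 tests), against 5% for a single test. For improvement only it is about 6-23% or 12-37%, against 2.5%. Results at n=10 are similar. Even with markers correlated at 0.9, the chance is more than twice the single-test figure.

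These sizes rest on the assumed t-tests, test counts and correlations. The absence of a lead marker, visit and success criterion does not depend on them. The null here is no change from baseline, which is not the same as no effect of Euflexxa. No control arm is described, and hyaluronate is both a listed marker and the injected substance. Those are separate points, and controlling multiplicity would not resolve them.

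The gap should be fixed before marker data are seen. The pilot can still run, and this point has no bearing on participant safety.

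**What to change.** In Data Analysis, before any marker data are seen, state that the marker panel is exploratory in this pilot and that the p ≤ 0.05 significance label does not apply to it. Also state that the change in every marker at both visits will be reported with a 95% confidence interval. This needs no new data. It gives up any formal efficacy claim from the markers, and the intervals will be wide, as the half-widths in the working show.

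If the sponsor wants one formal claim, it may instead name in advance one marker, one visit and that marker's direction of improvement, tested at two-sided 0.05, with all other marker comparisons descriptive. The documents do not settle that choice, so it is the sponsor's to make. By noncentral-t calculation, the change detectable with 80% power is 0.58 SD with 25 complete pairs and 1.00 SD with 10. A formal testing hierarchy across the remaining comparisons is hard to justify in an uncontrolled pilot of this size.

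Neither choice separates a treatment effect from other change over time. An assumed drift of 0.3 SD unrelated to treatment (noncentrality 0.3 × √25 = 1.5) would give a single pre-named marker p ≤ 0.05 in about 30% of 25-subject studies.

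### The clinical hypothesis allows up to 35 unadjusted tests with no deciding scale or visit, so the chance of a false improvement is about 0.2 to 0.5 instead of 0.025

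*Combined protocol and SAP*

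**What the plan says.** All references are to the combined protocol and SAP.

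- **Background and Significance.** After the biomarker hypothesis comes a second one: "we also hypothesize that Euflexxa therapy will improve pain, clinical outcomes, and time to total knee arthroplasty". It names no scale and no time point.
- **Secondary outcome measurements.** Pain is measured by VAS. A further item reads "The effect of Euflexxa on Clinical outcomes using the following standardized scales and questionnaires", followed by WOMAC, KSS, VR-12 and UCLA. The list is not ranked. The text above Table 1 and the table itself have SF-12 in place of VR-12.
- **Table 1.** All five scales are marked at Visit 1 and at Visits 2, 3, 4, 5, 6, 9 and 10, and not at Visits 7 and 8. The sentence above the table says that they "will be asked at each visit", which would add those two.
- **Data Analysis.** The section has two sentences. The first says that "all testing of statistical significance will be two-sided" unless otherwise indicated, and that "a difference resulting in a p-value of less than or equal to 0.05 will be considered statistically significant". No exception is indicated anywhere. The second says that "after each analysis, General Linear Models (GLM) will be used to control for possible confounders", naming BMI, gender, age and ethnicity.

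The section names no test, contrast, deciding scale or visit, multiplicity method or exploratory label. It does not say whether the unadjusted or the GLM p-value decides.

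**The concern.** The plan does not say which result would support the clinical hypothesis. Under the rule as written, a p-value of 0.05 or less on any scale at any visit may be called a statistically significant improvement, so 0.05 does not describe the error rate of the hypothesis.

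The visits also answer different questions. Visits 2 and 3 fall within the first injection course. Visits 4 and 5 follow it. Visit 6 is when the second course begins, and Visits 9 and 10 follow both courses. Differing results at Visits 3 and 6 need not contradict each other, but the plan does not say which of them bears on the hypothesis. That choice could be made after the data are seen.

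**Working it through.** The plan states no error rate, power or correlation for these outcomes, so there is no figure of its own to reproduce.

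**Inputs from the documents.** Five scales and seven post-baseline visits (Table 1); two-sided 0.05 (Data Analysis), hence 0.025 in the direction of improvement; 25 patients (Sample). The Injection paragraph also gives n=10, so that size was run too.

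**Assumptions.** No true change; normally distributed changes; paired t-tests of change from baseline; correlations as shown.

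**Step 1, count.** 5 × 7 = 35 possible tests, before subscales, GLM repeats and time to arthroplasty. If the scales were given at every visit, the count would be 5 × 9 = 45.

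**Step 2, independence as a bound.**
- Either direction: 1 − 0.95^35 = 0.834.
- Improvement only: 1 − 0.975^35 = 0.588.

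Independence cannot hold, because every change for a patient on a given scale uses the same baseline value. If a scale has equal correlation ρ between visits, two changes from one baseline have covariance 1 − ρ and variance 2(1 − ρ). Their correlation is therefore 0.5 whatever ρ is.

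**Step 3, simulation with the shared baseline.** n=25, 35 tests, visit correlation exchangeable at 0.5, 20,000 null trials per row:

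| Between-scale correlation | At least one false improvement | At least one p≤0.05, either direction |
|---|---|---|
| 0 | 0.468 | 0.739 |
| 0.3 | 0.399 | 0.702 |
| 0.5 | 0.357 | 0.656 |
| 0.7 | 0.301 | 0.572 |
| 0.9 | 0.216 | 0.424 |

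Against 0.025 for one pre-named test, this is 0.216/0.025 = 8.6 to 0.468/0.025 = 18.7 times nominal. With autoregressive visit correlation of 0.5 to 0.9, the ranges are somewhat lower: 0.167 to 0.432 for improvement and 0.338 to 0.700 in either direction. With n=10, false improvement ranges from 0.177 to 0.469 over all these settings, so the conflict over sample size does not change the conclusion.

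**Step 4, smaller families at n=25.**
- One scale over seven visits: false improvement about 0.12 with exchangeable visits, and 0.09 to 0.11 with autoregressive visits.
- Five scales at one visit: 0.118 at between-scale correlation 0, falling to 0.051 at 0.9. The independence formula gives 1 − 0.975^5 = 0.119.

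**Step 5, the second p-value.** If either the paired test or a GLM with centred covariates unrelated to the outcome may count, the two-sided error of one contrast rises from 0.05 to 0.054. The rule needs stating, but it adds little to the error rate.

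**Step 6, after the fix.** One pre-named scale at one pre-named visit gives 0.05 two-sided and 0.025 for a false improvement. Testing WOMAC only after VAS succeeds adds no error to that family. For comparison, keeping all 35 tests under Bonferroni would require 0.05/35 = 0.0014 per test.

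**The case against.** *The plan never says that each scale is tested at each visit.* This stands. Thirty-five is an upper count. One repeated-measures analysis per scale would also fit the text and would give about five tests, with a false-improvement chance of about 0.05 to 0.12. But nothing in the plan selects that analysis or rules out the others, and even the five-test reading is at least twice nominal.

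*A false improvement is more likely than not.* A reader might infer this from 35 tests at 0.05. The documents do not support it. The claim holds under independence (0.59), which the shared baseline rules out; with that baseline modelled, no setting reached one half. A chance above one half applies only to significance in either direction, which counts worsening too, and it fails even there when the scales are very highly correlated.

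*These are secondary outcomes in a pilot.* This also stands. The primary outcome is the aspiration biomarkers, and no confirmatory decision is said to depend on the scales. Strict familywise control would be more than the design needs. Even so, the plan states a directional hypothesis, applies a significance rule to all testing and labels nothing exploratory.

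*Controlling alpha leaves the larger threat.* This is correct. There is no comparator, and entry requires a VAS of 41 to 90 mm, so VAS may fall through regression to the mean. A reader might infer that a single pre-named test would establish a Euflexxa effect; it would not.

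**Conclusion.** The point holds as a gap in a secondary aim of an uncontrolled 25-patient pilot. The plan allows up to 35 tests at full two-sided 0.05 with nothing to say which one decides. With no true change, the chance of at least one false improvement is about 0.2 to 0.5 (between-scale correlation 0.9 to 0), and the chance of any significant result is about 0.4 to 0.75. Freedom to choose the visit for a single scale already gives about 0.12.

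These figures rest on assumed correlations, normal changes and visit-by-visit paired tests, none of which the plan specifies. The absence of a deciding scale and visit does not depend on them. The change should be made, but the biomarker aim is unaffected.

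**What to change.** In Data Analysis:

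1. Name one deciding clinical contrast: change in VAS from Visit 1 to Visit 6, with the Visit 6 value recorded before that visit's injection. Table 1 marks both at Visit 6 and does not state their order. This contrast matches the 26-week VAS result that the Background cites from the earlier saline-controlled trial.
2. Test WOMAC change at Visit 6, on one named WOMAC score, at 0.05 only if VAS is significant.
3. Report KSS, VR-12/SF-12, UCLA and all other visits as exploratory estimates with 95% confidence intervals and no significance claims.
4. State that the unadjusted within-patient test decides and that the GLM, with centred covariates, is a sensitivity analysis.
5. State that, with no comparator and entry restricted to VAS 41 to 90 mm, a significant VAS change is a change from baseline that may include regression to the mean, not a demonstrated Euflexxa effect.

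Also reconcile VR-12 with SF-12, the sentence above Table 1 with the table, 25 patients with n=10, and the Visit 6 window (±2 weeks under Aspiration, ±4 weeks in Table 1).

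The cost is a few sentences, with no new patients or data. The downside is that nominally significant results on other scales or at other visits can be reported only as exploratory.

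### The only model named for the two-year clinical scales is a GLM with no missing-data rule; if patients leave for lack of benefit, the 1- and 2-year means would favour Euflexxa

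*Combined protocol and SAP*

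**What the plan says.** The Data Analysis section has two sentences. The first sets two-sided testing, where "a p-value of less than or equal to 0.05 will be considered statistically significant". The second says that after each analysis "General Linear Models (GLM) will be used to control for possible confounders, including BMI, gender, age and ethnicity". The analyses that the GLM follows are not named, and the plan does not say whether it is fitted visit by visit or as repeated measures.

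Study Design gives "25 subjects for a pilot study". The Injection paragraph reads "Twenty five patients will be assigned to receive Euflexxa (n=10) (1% sodium hyaluronate", with no comparator. The two counts in that sentence must be reconciled; the working below uses 25.

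The secondary outcomes begin with "The effect of Euflexxa on pain, using the Visual Analogue Scale (VAS" and continue with WOMAC, KSS, VR-12 (SF-12 in Table 1) and UCLA. Table 1 schedules these scales at Visits 1-6, 9 and 10. After month 6 the only scoring visits are "Visit 9 (1-year±2 months" and the 2-year visit. Surgery to the knee is asked about at the same visits. The primary outcome, aspiration for biomarkers, is scheduled only at Visits 1, 4 and 6.

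No part of the document states an analysis set, a denominator, an expected drop-out rate, a treatment of missing scores, or a rule for scores recorded after knee arthroplasty.

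**The concern.** An ordinary GLM cannot use a record without an outcome. Fitted per visit, it describes whoever attended. Fitted as a classical repeated-measures model, it deletes any patient who misses one of the eight scoring visits. Unless the plan says otherwise, one of these becomes the analysis.

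In a randomised trial, similar loss in both arms can partly cancel. Here there is one arm and the estimate is a change from baseline, so any link between leaving and response passes straight into the result. The study hypothesises better pain and clinical outcomes. At 1 and 2 years that would be judged on a subset of the 25 whose composition the plan neither controls nor requires to be described.

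**Working it through.** **Plan's own figure.** There is none to reproduce: no SD, drop-out rate, effect size or power accompanies the 25. All inputs below other than n, the visits and the 0.05 level are assumptions. Negative values mean less pain.

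**1. Algebra.** Bias of the attenders' mean = d × Δ in size, where d is the share missing and Δ is how much worse leavers are than stayers. With Δ from 10 to 30 mm on VAS:

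| Missing | d | Bias towards benefit |
|---|---|---|
| 2 of 25 | 0.08 | 0.8 to 2.4 mm |
| 5 of 25 | 0.20 | 2 to 6 mm |
| 10 of 25 | 0.40 | 4 to 12 mm |

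It is zero if d = 0 or Δ = 0, and changes sign if leavers are better.

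**2. Retention under one drop-out model.** Assume a between-patient SD of 18 mm and a within-patient SD of 15 mm, so the SD of change is √(18² + 15²) = 23.4 mm. Three intervals run from month 3 to year 2. The risk of leaving in each is 15-35% if the last score improved by less than 10 mm, and 5% otherwise. With true mean change 0 at every visit:
- P(improved by less than 10 mm) = Φ(10/23.4) = 0.665.
- Risk per interval = 0.665 × 0.15 + 0.335 × 0.05 = 0.117, up to 0.665 × 0.35 + 0.335 × 0.05 = 0.250.
- Remaining at 2 years ≈ 25 × 0.883³ = 17.2, down to 25 × 0.750³ = 10.5. Simulation gives about 17 and 11, because those who stay increasingly have low risk.

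**3. Simulated 2-year VAS change, same model, n = 25.** Each range runs from the 15% to the 35% risk.

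| Situation | Bias of attenders' mean | Bias of likelihood estimate |
|---|---|---|
| Poor responders leave, truth 0 mm | about -1.7 to -6.0 mm | within about 0.4 mm |
| Poor responders leave, truth -10 mm | about -1.8 to -6.1 mm | about 0.1 mm |
| Loss unrelated to response | about 0 | about 0 |
| Patients who feel well leave, truth 0 mm | about +1.6 to +4.9 mm | close to 0 |
| Leaving depends on the unseen score, truth 0 mm | also towards benefit | about -0.5 to -2.4 mm remains |

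In the first row a significant improvement is declared in about 5-12% of trials instead of 2.5%. For scale, the standard error is about 23.4/√17.2 = 5.6 mm at the mild end and 23.4/√11 = 7.1 mm at the severe end. The bias is therefore about 0.3 to 0.85 of a standard error.

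**4. A different model.** Take 6- and 12-month changes with SD 25 mm, correlation 0.5 or 0.7, and 20% loss. If leaving depends on the observed 6-month score, the attenders' mean is off by -3.1 to -4.3 mm and the likelihood estimate by about 0. If it depends on the unseen 12-month score, the figures are about -6.2 mm and -3.5 to -4.9 mm.

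**5. Complete-case fit.** Assume independent attendance of 95% or 90% at each of the 7 post-baseline scoring visits. The number kept is 25 × 0.95⁷ = 17.5 or 25 × 0.90⁷ = 12.0. Confidence intervals widen by 1/√0.698 = 1.20 or 1/√0.478 = 1.45. This loss of precision occurs even if attendance is random.

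**The case against.** The strongest objection is that the defect is silence, not a stated choice. The plan nowhere restricts the model to attenders, and the GLM is described as a follow-on adjustment. A reader might infer that the plan prescribes an observed-case analysis; it does not. That stands, and the point rests only on what a GLM does by default when no rule is given.

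A reader might also infer that Euflexxa will look better than it is. The documents give neither a drop-out rate nor a reason for leaving, and the working shows zero bias under random loss and a reversed bias if patients who feel well leave. The direction is conditional.

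The stipend might be read as evidence that drop-out is expected. It is 40 dollars per visit, followed by the sum: "a total of 400\$ will be paid to the patient if all the visits are completed". This allows for missed visits, but it equally serves retention, as does free parking. The exclusion of conditions that might interfere with completion works the same way. None of this gives a rate, and none of it guarantees that all 25 attend at 2 years.

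Finally, a mixed model is no complete cure. Its near-zero bias in the simulation depends on leaving being driven by observed scores and on variance components taken as known. When leaving depends on the unseen score, bias remains. This also stands, and is why the fix includes a sensitivity analysis.

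**Conclusion.** The concern holds in conditional form. The one named model, with no analysis set or missing-data rule, leaves the 1- and 2-year clinical means open to selective loss that nothing in a single-arm design offsets. If poor responders leave more often, the VAS bias is about -2 to -6 mm with roughly 11-18 of 25 patients remaining, under the assumed SDs and drop-out risks. Those inputs are illustrative, and milder drop-out gives less.

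The affected outcomes are secondary. It would be wrong to extend the 1- and 2-year argument to the primary biomarkers, because none are collected after 6 months. In a 25-patient pilot this should be changed, since the remedy uses data already scheduled, but it does not undermine the study as a whole.

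**What to change.** In Data Analysis, for VAS, WOMAC, KSS, SF-12/VR-12 and UCLA:

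1. Define the analysis set as all patients who received at least one injection.
2. Replace the GLM by a likelihood-based mixed model for repeated measures fitted to every observed score, with visit as a factor, baseline among the responses and the planned covariates kept. Name the covariance structure: an unstructured one for eight visits has 8 × 9/2 = 36 parameters, too many for 25 patients, so a simpler structure is needed.
3. Report the number with a score at each visit, and record the reason when a patient stops attending.
4. Add a sensitivity analysis of the same mean in which patients without a 1- or 2-year score are assumed worse by a range of shifts, for example 0 to 30 mm on VAS. The estimate moves by d × shift. With 7 to 14 of 25 missing, a 30 mm shift moves it by 0.28 × 30 = 8.4 mm to 0.56 × 30 = 16.8 mm, so the reader can see where the conclusion changes.
5. State how scores recorded after knee arthroplasty are handled in the analysis. A patient who has surgery may stay and supply scores, and the mixed model would otherwise include them without comment.

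The cost is SAP wording and somewhat more analysis, with no extra visits or patients. The 1- and 2-year figures may look less favourable.
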